# Assessments

QUESTIONNAIRES FILLED IN BY PARENT PRIOR TO HOME VISIT BY RESEARCHER:

a) CONCERNING CHILD (Parent report)

Strengths and Difficulties Questionnaire (Goodman 1997)

Eyberg Child Behaviour Inventory (ECBI)

IRAS ID 268597 PPC RCT Protocol v6.0 12.02.25

Social Communication Questionnaire (SCQ) (Rutter et al, 2009)

Inventory of Callous-Unemotional Traits (ICU) (Frick, 2014)

Quality of attachment relationships questionnaire (QUARQ) (Briskman et al, 2012)

Adapted Affective Reactivity Index (Stringaris et al 2012)

Child Health Utility 9D quality of life measure (CHU9D)

## b) CONCERNING PARENTS/ FAMILY

Confusion, Hubbub and Order Scale (CHAOS) (Matheny, Wachs, Ludwig, & Phillips, 1995)

Short Alabama Parenting Questionnaire (APQ) (Scott et al, 2011)

Brief Self-Efficacy Parenting Scale (Woolgar, 2015)

Generalised Anxiety Disorder Assessment (GAD-7)

Patient Health Questionnaire (PHQ-9)

Relationship with Partner (Moffitt)

Parent Personality SCID-II

Parent alcohol use (AUDIT)

Parent drug use (DUDIT)

#### TOTAL PARENT QUESTIONNAIRE TIME 80 minutes

#### QUESTIONNAIRE FILLED IN BY TEACHER

Strengths and Difficulties Questionnaire (Goodman 1997)

#### INTERVIEW WITH PARENT BY RESEARCHER

Parent Account of Child Symptoms Interview (PACS) include EE rating

Primary Outcome Measure (Taylor et al., 1997)

Child and Adolescent Service Use Schedule (CA-SUS)

Visual analogue scale of 3 main concerns about child (Scott, 2001)

#### TOTAL INTERVIEW TIME 80 minutes

# ASSESSMENT OF CHILD BY RESEARCHER 2 DURING HOME VISIT

York Assessment of Reading Comprehension (YARC)

## TOTAL CHILD ALONE ASSESSMENT TIME 50 minutes

# ASSESSMENT OF PARENT WITH CHILD BY RESEARCHER 2 DURING HOME VISIT

Observation of parent-child interaction (Matias et al 2014)

#### TOTAL PARENT-CHILD INTERACTION TIME 25 minutes

#### 6. INTERVENTIONS

Participants will be randomly allocated to one of two groups:

Group 1: Waiting list followed by Parent-Led Education and support (PLES) designed to provide parents with support in parenting a child with persistent conduct problems. Research into parents' preferences for how to receive help indicate that many prefer self-administered formats (Metzler, Sanders et al., 2012). Following initial assessment, families randomised to this arm of the trial will wait 16 weeks and then be re-assessed before receiving the treatment. Inclusion of this waitlist period will enable the study to answer the question whether 1) the more intensive treatment is superior to no treatment (the primary aim of the trial) and also, as a secondary analysis, 2) whether the PLES intervention is superior to no treatment (waitlist). The study team will maintain close and frequent contact with the families while they are awaiting treatment and provide a contact number should they wish to speak to one of the researchers. NIHR and the programme steering committee have approved this change. Currently this population receive no treatment at all so it is felt that this is ethical. The PLES condition in this study will provide parents with a range of self-administered formats (see below) with additional advice being provided weekly by a CAMHS practitioner, in response to parents' own questions. Parents will have access to an online parenting programme which covers key aspects of parenting skills which have been shown to be effective in reducing child behaviour problems. The practitioner will be familiar with the online programme and will be available to talk over parents' questions about it. Parents will also be provided with other sources of information regarding children and their parents, such as books, and specifically prepared reading, which cover topics which are additional to the online programme and provide alternative approaches. These include reflecting on children's thoughts and feelings, and how parents decide when to listen, when to comfort, and when to ensure they behave as expected. The practitioner will be available to talk over all the written and online materials. It is also designed to be an informative and cheaper alternative to the intensive personalised programme, PPCP, so that a finding of no difference between the intervention arms will have service implications. A trained practitioner will be assigned to the parents over a 16 week period, so that they can meet, where possible online, every week.

Group 2: **The Personalised Programme for Children and Parents** (PPCP) is a manualised programme based on evidence-based theories, including social learning theory and attachment theory. It is a strength based, active outreach approach. The starting point is parent defined concerns and goals. Detailed assessment of child problems and related family issues will provide an informed basis for developing the intervention. The programme is adjusted and tailored throughout, based on parental feedback and routine monitoring, using standardised measures. It employs key interventions that have been shown to reduce child conduct problems including collaborative working, active rehearsal and coaching.

The programme is separated into modules which will be selected and ordered in line with parental priorities and concerns. It is anticipated that the programme will normally include sections from the joint parent and child module. The modules are:

- 1. Individual parent: Focusing on parent wellbeing and emotional regulation
- 2. Parents working together: Joint couple sessions focusing on couple communication, problem solving and working together on child nurture and behaviour management
- 3. Joint parent(s) and child. Parent(s) and child sessions, using active rehearsal and coaching in play sessions. Sections will be chosen according to need and include:
- a) Nurture and mutuality to strengthen parental sensitivity and parent-child mutuality
- b) Praise and reward
- c) Limit setting and compliance
- d) Using consequences effectively

- e) Problem solving with children
- 4. Parent(s) and School: Helping parents to improve communication and establish joint goals and plans for their child with school.

The programme will have 12-24 sessions, according to family needs and preference. Sessions will be clinic-based or home-based, according to parent(s) wishes. If additional services are needed, PPCP therapists will help the family access those services and work collaboratively with them. The primary endpoint is after 16 weeks.

The practitioners who administer the interventions will be recruited separately from the research team. They will be qualified CAMHS practitioners, recruited through the standard NHS recruitment services. On appointment, they will undergo initial intensive training for 3 days, followed by weekly supervision by the Trial Clinicians in accordance with a detailed manual.

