## 4.2 Revised Study Plan

In discussion with the funder it was decided to stop recruitment on 31st August 2024 despite not reaching the intended sample size. It was agreed to follow up participants to 16 weeks and then lock these data and analyse only the 16 week outcomes as part of the NIHR funder report. We will formally report on outcome differences between PPCP and waitlist arms at 16 weeks. 32 week outcomes will be collected beyond the end of the original funding period which was 31st April 2025; data will now be collected until 31st August 2025. By necessity future analyses of differences with PLES will not be blind. Depending on attrition rates it might also be only possible to provide descriptive analyses involving the PLES arm. However, the team is committed to ultimately publishing all outcome data collected as part of this study.

By the end of December 2024, we had recorded the outcomes of 80 trial participants at the 16-week-from-randomisation stage. This means that comparisons will be made between 40 participants who have completed the PPCP intervention and 40 participants who have been on the waiting list, which is the primary outcome objective.

[figure not shown]
However, in view of the revised sample size (numbers of participants being around 30-40% of those predicted) the study may be better described as a Pilot and Feasibility Study, rather than a full RCT.

NIHR has agreed a proposal to conduct two additional qualitative interviews exploring the experience of study participants and that of the practitioners in order to optimise learning for the NHS. These will be conducted and analysed as described in Section 7.3 Process Evaluation.

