#### Notes:

#### Measures

The PACS semi-structured interview of conduct problems is the primary outcome measure and is a more precise instrument than questionnaires. However, we have included the Eyberg Child Behaviour Inventory since it is widely used in studies across the world, particularly in the USA. The Strengths and Difficulties Questionnaire gives a more broad measure of well-being but is not a formal outcome. The Visual Analogue Scale is important since the parents define the problem so this is more personalised than the symptom count.

The Short Alabama parenting questionnaire measures the proximal target of the intervention, namely parenting style.

The measures marked C for Clinical are to help characterise the clinical nature of the sample.

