#### 5 METHODS of DATA COLLECTION

Assessments will be conducted on each of the two sites by two Research Assistants. Supervision and assistance will be provided by the Research Coordinator based at the Tavistock Clinic. Assessments will be completed at baseline prior to randomisation and then at 16 and 32 weeks for PPCP and 16, 32 and 48 weeks for PLES. Parents will be sent a link to an online survey (or a paper pack of questionnaires if they prefer) prior to their first meeting with the research assistants and the assistants will support their completion as required. Assessment time points are shown in the flow diagram (see section 4.2 Assessments). The primary end point is 16 weeks after the baseline assessment.

The screen will be the conduct problem sections of the Parent Account of Child symptoms interview, administered by a researcher.

Baseline assessments will include measures on: Demographics, Medical history, Child behaviour including the Primary Outcome Measure (PACS Conduct Section), and Eyberg and SDQ, Co-morbid diagnoses (PACS and SCQ), Child characteristics (ICU and YARC), Parental well-being and parental relationship (GAD-7, PHQ-9), Parenting (Alabama and Self Efficacy). Parents will be asked for their consent for researchers to make an audiovisual recording of parents and children during the Parent/Child observation interaction, and to make an audio recording of the PACS parent interview.

To compensate parents for the time they spend completing questionnaires and being interviewed, we will give them £40 of vouchers for the initial and final assessments, and £10 for completing the interim assessment. We will also refund any travel expenses they might incur as part of the study.

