# 9.2.2 Randomisation procedures and blinding arrangements

Randomisation of parent/child dyads to waitlist/PLES or PPCP trial arms will be at the individual dyad level with 50% of dyads randomised to either arm. Within parent subpopulation ("decliners" or "non-responders to group approaches") we will use randomly varying block sizes to ensure that the times when dyads start on their allocated groups also balances across trial arms. Randomisation will be provided online vis an independently monitored computer system set up by the accredited Clinical Trials Unit at King's College (KCTU).

The procedure is as follows: Each participant will be allocated a unique, anonymised ID number King's College London Clinical Trials Unit. Details will be entered into the KCLTU randomisation system. The outcome of allocation will be communicated to the trial's senior clinical supervisor, [name], who will then arrange for either a PPCP therapist (intervention arm) or PLES therapist (comparison arm) to make contact with the allocated participant in order to communicate the next steps.

Other members of the research team (including the Chief Investigator, senior statistician and research assistants) will remain blind to participant allocation status throughout the trial. As a result of the change in study design and the analyses of 16-week outcome data before locking the 32 week data collection blinding it is now only possible for the 16-week outcome collection and analyses to remain blind, but not for any 32-week outcome data.

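### Waiting-list contact by the study team conflicts with blind outcome assessors, and 32-week assessor blinding is given up for a reason that covers analyses only

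*Protocol*

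**What the plan says.** **Contact during the wait.** Section 6, Group 1: "The study team will maintain close and frequent contact with the families while they are awaiting treatment and provide a contact number", to be used "should they wish to speak to one of the researchers". Families in Group 2 start PPCP at once, so this provision applies to one arm only.

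**Blinding.** Section 9.2.2 sends the allocation to the senior clinical supervisor, who arranges for a PPCP or PLES therapist to approach the family. It then says: "Other members of the research team (including the Chief Investigator, senior statistician and research assistants) will remain blind to participant allocation status throughout the trial".

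**Who assesses.** Section 5: "Assessments will be conducted on each of the two sites by two Research Assistants". The same section places the PACS among the interviews that a researcher holds with the parent. The Measures notes say: "The PACS semi-structured interview of conduct problems is the primary outcome measure and is a more precise instrument than questionnaires".

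**32 weeks.** Because 16-week data are analysed before the 32-week data are locked, Section 9.2.2 concludes that "it is now only possible for the 16-week outcome collection and analyses to remain blind, but not for any 32-week outcome data". Section 4.2 (Revised Study Plan) is narrower: "By necessity future analyses of differences with PLES will not be blind".

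**The concern.** Parents in a waiting-list trial know their arm and supply the account on which the PACS is scored. Interviewer blinding therefore cannot prevent reporting bias. What it can limit is rating bias: how the interviewer probes and scores that account. If the interviewer knows the arm for waitlist families, a shift in rating enters the PPCP versus waitlist contrast at 16 weeks and cannot be told apart from a treatment effect. That contrast is the primary result and the only one to be formally reported now.

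The 32-week statement has a smaller reach. Section 7.1.2 compares PPCP at 16 weeks with PLES at 32 weeks. If 32-week collection is unblinded, ratings made under blinding are set against ratings made without it, so the difference in masking lies inside the comparison.

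**Working it through.** The conflict is settled by setting the sections side by side. Arithmetic is used only to show scale.

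**1. Does the contact reveal the arm?** Section 4.1 gives two arms: 16 weeks of waiting and then PLES, or 16 weeks of PPCP. Only the first arm waits for treatment. Anyone who keeps up contact with a family because it is waiting knows its allocation.

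**2. Can the people in contact be the raters?** Section 6 names the study team and offers a researcher. Under Group 2, the same section says that practitioners are recruited separately from the research team, so the plain sense of researcher is not a practitioner. Section 5 uses the same word for the person who conducts the PACS interview, with two research assistants per site. No section says that those making contact are kept apart from those who rate.

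**3. Is this compatible with 9.2.2?** Not as written. The research assistants must be blind for the whole trial, while the team they belong to is given a task that discloses one arm.

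**4. Does the reason given for 32 weeks support the conclusion?** Analysing 16-week data by arm unblinds the analysts and anyone who sees arm-labelled data. It does not tell an interviewer which arm a particular family is in. Section 4.2 (Revised Study Plan) claims necessity for analyses only; Section 9.2.2 extends it to collection. Section 9.2.2 also contradicts itself, since the sentence before still promises blinding throughout.

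**5. Scale.**
- Plan's own figure (9.2.1; 0.4 SD, 80% power, alpha 0.05, taken as two-sided): n per arm = 2 × (1.960 + 0.842)² / 0.4² = 98.1, rounded up to 99, so 198 in total; 198 / 0.8 = 247.5, so 248. Both stated figures reproduce and do not bear on this point.
- Implied SD (9.2.1): 0.16 points / 0.4 = 0.40 PACS points.
- Numbers at 16 weeks (4.2, Revised Study Plan): 40 versus 40. Standard error of the difference in SD units = √(2/40) = 0.224.
- Assumption: a mean rating shift b in favour of PPCP over the whole waitlist arm, and no true effect. The protocol gives neither a size nor a direction, so a range is shown.
- Two-sided type I error = Φ(b/0.224 − 1.960) + Φ(−b/0.224 − 1.960).

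| b (SD) | PACS points | Share of 0.4 SD target | Type I error |
|---|---|---|---|
| 0.1 | 0.04 | 25% | 7.3% |
| 0.2 | 0.08 | 50% | 14.6% |
| 0.3 | 0.12 | 75% | 26.9% |

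The t distribution gives 7.3%, 14.3% and 26.3%. If only some waitlist ratings are exposed, b shrinks in proportion: 0.2 SD in half of them is a mean shift of 0.1 SD.

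**6. Timing.** Recruitment stopped on 31 August 2024. If the last family was randomised that day, 16 weeks ended about 21 December 2024 and 32 weeks about 12 April 2025. The protocol version is dated 12 February 2025, and 32-week collection is allowed until 31 August 2025. The waiting periods were therefore essentially over at this version, while some 32-week visits were still to come.

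**The case against.** **On the waiting period.** The protocol never says that research assistants or PACS raters make the contact. The study team could mean people who already know the allocation, and 9.2.2 provides such a route through the supervisor and therapists. A telephone number by itself is not specific to an arm, since 9.2 offers a trial number to parents generally. The service-use interview (CA-SUS), held in the same researcher interview, may also reveal treatment in either arm. All of this is fair. It means that loss of blinding is possible under the text but not shown to have happened, and that changing the contact person would not remove every cue. It does not remove the conflict, because the text points to researchers and writes no separation.

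**On 32 weeks.** A reader might infer that assessor blinding was given up without need. The documents do not support that. At 32 weeks PPCP families have Pack C, with the observation and reading test, and PLES families have Pack B, with a further visit at 48 weeks. Those extra items belong to a second researcher, but with two assistants per site that colleague's attendance is itself a sign of the arm. The voucher for a final visit also differs from that for an interim one. What stands is narrower: the reason that 9.2.2 gives does not lead to its conclusion on collection. Only secondary comparisons are touched, and Section 4.2 (Revised Study Plan) says that they may be descriptive.

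**On the remedy.** Repeating the primary model without ratings by people who had been in contact may look like the natural sensitivity analysis. It would remove families from the waitlist arm only, selected after randomisation, and could remove much of a group of 40. It would break the randomised comparison and should not be done.

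**Conclusion.** The concern holds in two parts of unequal weight. The main one is a contradiction between Section 6 and Section 9.2.2 that leaves the primary 16-week PACS open to rating bias in one arm. A reader might go further and infer that the 16-week ratings were in fact unblinded, or are biased. The protocol does not say who made the contact, so that cannot be concluded; nor does it support describing these ratings as assessor-blind without a check. The sizes rest on an assumed drift of 0.1 to 0.3 SD, in favour of PPCP, with 40 per arm and no true effect: 25% to 75% of the target effect, and type I error of about 7% to 27%. They concern rating bias alone.

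The lesser part is that 9.2.2 gives up blind 32-week collection on grounds that justify unblinded analyses only. Because visits differ by arm, masking there could only ever have been partial.

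**What to change.** 1. **Section 6.** State that waiting-period contact and the contact number go through staff who already know allocation (the senior clinical supervisor and PLES practitioners), and that the PACS is rated by a research assistant who had no waiting-period contact with that family. For this cohort the change mostly sets the record straight, as the waits were nearly all over.
2. **16-week ratings already made.** From the contact records, state who made the contact and whether they rated the PACS. Report the number of ratings that may have been unblinded. Do not call the 16-week PACS assessor-blind where this cannot be shown. Keep all ratings in the analysis.
3. **Remaining 32-week visits.** Limit the stated loss of blinding to analyses, withhold allocation and arm-labelled data from assessors, and acknowledge that Packs B and C may reveal the arm.
4. **Section 9.2.2.** Remove the promise of blinding throughout the trial, or reconcile it with the sentence that follows.

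The cost is wording, a review of contact records and a small administrative load on the supervisor and practitioners. Practitioner contact during the wait would need to stay separate from PLES itself, since the waitlist is the no-treatment comparator. The published blinding statement may be less favourable than the present one.

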### 7. METHODS of DATA ANALYSIS

#### 7.1 Quantitative Analysis

# 7.1.1 Primary Analysis

The original plan based on meeting the recruitment target and having access to a locked database containing relevant baseline, 16 week and 32 week variables was as follows:

All analysis will be according to the intention-to-treat principle. Characteristics of the treatment groups will be described at baseline. Preliminary analysis will investigate the pattern of missing outcome data. The statistical analyses of the primary outcome measure (PACS) and the secondary measures will estimate three treatment effects to address the primary and secondary objectives of this study. Briefly, we use linear mixed models to estimate relevant contrasts. Continuous outcome variables such as PACS will be analysed in long format, for example the PACS variable will consist of stacked measures of (i) PACS recorded at baseline in either arm, (ii) PACS recorded at 16 weeks in either arm, and (iii) PACS recorded at 32 weeks in the waitlist/PLES arm only. The models will contain a dummy variable for PPCP trial arm (PPCP), a dummy variable for the 16 week assessment time point (W16), the product of these two dummy variables (PPCP x W16), and a dummy variable indicating the 32 week assessment time point in the waitlist/PLES arm (W32), binary participant sex and continuous age as known predictors of outcomes, dummy variables for delivering PLES or PPCP interventions and randomisation stratifiers. With this parameterisation the regression coefficient of PPCP x W16 represents the treatment effect of PPCP vs waitlist at 16 weeks; and the other treatment effects can be estimated by estimating relevant contrasts of the regression coefficients. To account for the correlation between the two or three repeated measures on the same participant (and to acknowledge that the contrast between waitlist and PLES is a within-trial arm comparison) a subjectvarying random intercept will be included.

The analyses will remain valid in the presence of missing values in the outcome variables, provided the variables that predict missingness are included in the respective linear mixed model (missing at random, MAR, assumption).

After it was agreed with the funder to stop recruitment and only formally report on the PPCP vs waitlist comparisons at 16 weeks as part of this study, the SAP had to be amended. Specifically, the proposed analyses were simplified so that they could be carried out after the 16 week data was locked (i.e. not requiring access to any 32 week data:

All analysis will be according to the intention-to-treat principle. Characteristics of the treatment groups will be described at baseline. Preliminary analysis will investigate the pattern of missing outcome

data. The statistical analysis of the primary outcome measure (PACS) and the secondary measures (ECBI etc) will estimate the effect of PPCP relative to waitlist at 16 weeks post randomisation. Briefly, we will use an ANCOVA approach to estimate relevant trial arm differences. The models will contain a dummy variable for the PPCP trial arm and include covariates for binary participant sex and continuous age as known predictors of outcomes and for the randomisation stratifier.

These simplified analyses will remain valid in the presence of missing values in the outcome variables, provided the variables that predict missingness are included in the respective linear mixed model (missing at random, MAR, assumption).

A full statistical analysis plan (SAP) will be developed by the trial statisticians and agreed with the principal investigators and TSC before any post randomisation data is seen by either party.

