#### 9.2.1 Size of trial sample

The trial aims to recruit and randomise 248 parent/child dyads. Half of the total number recruited (estimate 124) will be randomised to each arm of the trial. This sample size has been calculated on the basis of a PACS 16 week difference between the mean scores of the PPCP and waitlist groups of 0.4 standard deviations, based on an independent samples t-test with 80% power and alpha=0.05 (sample size required = 198), and is inflated for an anticipated 20% attrition rate (Scott et al 2001; Scott et al 2010). This is a conservative estimate, our previous trial with a clinical population got an effect size of 1.06 standard deviations compared to a wait list control (Scott et al 2001). A standardised effect size of 0.4 amounts to a PACS difference of 0.16 points. We consider such a difference clinically significant because any numerous studies it has been associated with clinically significant reduction in child aggressive and antisocial behaviour, improved school attendance and a happier family atmosphere. Also these improvements have been retained at longer term follow-up over several years (Scott et al 2014).

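### The amended ANCOVA in Section 7.1.1 names no baseline outcome score as a covariate, giving up precision that already-collected data would recover

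*Protocol*

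**What the plan says.** Section 7.1.1 of the protocol holds two plans. The superseded one was a long-format linear mixed model in which "PACS recorded at baseline in either arm" was one of the stacked responses. The amended one is an ANCOVA for PACS and the secondary measures at 16 weeks. Its models contain an indicator for the PPCP arm and "include covariates for binary participant sex and continuous age as known predictors of outcomes and for the randomisation stratifier". No baseline score appears among these terms.

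The reason given for simplifying is that the analysis can then be run on the locked 16-week data, "not requiring access to any 32 week data". Section 5 confirms that the baseline assessment covers "Child behaviour including the Primary Outcome Measure (PACS Conduct Section", and the measures pack for the assessment before randomisation lists PACS, ECBI and the other outcome scales.

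The missing-data sentence that follows the ANCOVA still makes validity depend on which variables are in a linear mixed model. The section ends by referring to a full SAP, which is not shown.

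**The concern.** Baseline PACS is the same interview given 16 weeks earlier, so it is a natural candidate for the strongest available predictor of the primary outcome. Avoiding 32-week data is no reason to leave it out. Section 4.2 (Revised Study Plan) leaves about 40 families per arm, against 124 per arm planned, so precision is scarce. Section 9.2.2 stratifies randomisation only by parent subpopulation, so the design does not balance baseline severity, and the named covariates do not adjust for it.

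The choice affects the primary estimate, every secondary estimate, and the PPCP versus PLES comparison in Section 7.1.2, which borrows the updated primary method. It also affects the missing-data claim: baseline severity could plausibly predict dropout, and it is not among the variables named.

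**Working it through.** **Inputs from the protocol**
- Effect size (Section 9.2.1): "difference between the mean scores of the PPCP and waitlist groups of 0.4 standard deviations".
- Test (Section 9.2.1): "based on an independent samples t-test with 80% power and alpha=0.05 (sample size required = 198". Sidedness is not stated; two-sided reproduces the figure.
- Scale (Section 9.2.1): "A standardised effect size of 0.4 amounts to a PACS difference of 0.16 points", so the implied SD is 0.16/0.4 = 0.40 points.
- Attrition (Section 9.2.1): the size is "inflated for an anticipated 20% attrition rate".
- Families with 16-week outcomes (Section 4.2): 40 per arm.

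**Assumption.** r is the within-arm correlation between baseline and 16-week score, given sex, age and stratifier. The protocol gives no value, so 0.3 to 0.7 is shown. The entry rule of PACS at or above 1.32 (Section 9.1.1) truncates the baseline range and may lower r.

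**Step 1: the plan's own figure.** n per arm = 2(1.960 + 0.842)²/0.4² = 98.1, rounded up to 99, so 198 in total (an exact t calculation gives 99.08 per arm). Then 198/0.8 = 247.5, which rounds up to 248. Both stated numbers reproduce.

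**Step 2: the amended model as named.** At 40 per arm the SE is √(2/40) = 0.224 SD. Power for 0.4 SD by exact t is 42%. The detectable difference at 80% power is 0.63 SD. The 95% CI half-width is 1.99 × 0.224 × 0.40 = 0.18 PACS points, slightly more than the 0.16 target.

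**Step 3: add the baseline score.** The residual SD is multiplied by √(1 − r²), and the equivalent number of families is 80/(1 − r²). The last column is the two-time-point version of the superseded mixed model. Because that model has a free arm term at baseline, its treatment effect is a difference in mean change. With equal variances its SD multiplier is √(2(1 − r)).

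| r | SE reduction | Power, no baseline | Power, baseline-adjusted ANCOVA | Equivalent families | Power, change contrast |
|---|---|---|---|---|---|
| 0.3 | 5% | 42% | 46% | 88 | 32% |
| 0.4 | 8% | 42% | 49% | 95 | 36% |
| 0.5 | 13% | 42% | 53% | 107 | 42% |
| 0.6 | 20% | 42% | 60% | 125 | 51% |
| 0.7 | 29% | 42% | 70% | 157 | 63% |

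The detectable difference at 80% power falls from 0.63 SD to 0.55 SD at r = 0.5 and to 0.45 SD at r = 0.7.

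**Step 4: compare the three models.** Their variances are proportional to 1 (no baseline), 1 − r² (ANCOVA with baseline) and 2(1 − r) (change contrast). Since 2(1 − r) − (1 − r²) = (1 − r)², the change contrast is less precise than baseline-adjusted ANCOVA for every r below 1. It is also less precise than no adjustment when 2(1 − r) exceeds 1, that is, when r is below 0.5.

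**Step 5: chance imbalance.** The SE of the baseline difference is also 0.224 SD. At r = 0.6, an imbalance of one SE moves the unadjusted estimate by 0.6 × 0.224 = 0.13 SD, or about 0.05 PACS points. Only the fraction r passes through, and this variation is already inside the unadjusted SE of Step 2. It is the same cost seen another way, not a second one.

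**The case against.** The best defence is that Section 7.1.1 gives only a brief account and refers to a full SAP. In trials, ANCOVA often means a follow-up score adjusted for its own baseline, so the sentence may be naming only the additional covariates. This stands to a degree: a reader should not infer that the protocol gives a complete specification, or that the analysis actually run will omit the baseline. But the text says what the models contain, down to age and sex, and following it literally gives a model without baseline. If the SAP does include it, the protocol sentence still needs to be brought into line.

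Three stronger readings are tempting and are not supported.
- *The omission gives up much of the trial's precision.* At r = 0.3 the gain is about 4 power points. It is large only towards the top of an assumed range.
- *The amendment discarded a more precise analysis.* The superseded model used baseline as a response with a free arm term, not as a covariate. The amended model as named is less precise than that one only if r exceeds 0.5.
- *The primary estimate is biased.* With complete data, randomisation protects the comparison, and the stated SE already allows for chance imbalance.

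It is also fair to say that adjustment does not rescue the test. Power stays below 80% even at r = 0.7, and Section 4.2 itself suggests that the study may be better described as pilot and feasibility work.

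**Conclusion.** The point holds as a matter of efficiency and clear specification, not of validity. The protocol names the covariates of its primary and secondary models and does not name the baseline outcome, although the score is available and the stated reason for the amendment gives no ground for leaving it out.

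For 0.4 SD at 40 per arm, two-sided 5%, adding baseline PACS lowers the SE by 5% to 29% and raises power from 42% to between 46% and 70%, for r between 0.3 and 0.7. That range is an assumption. The figures also take 40 analysed families per arm, equal variances, and no allowance for variance explained by sex, age or stratifier.

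The missing-data sentence is a separate small error: it refers to a linear mixed model that the amended plan no longer uses. If dropout depends on baseline severity, the named covariates do not meet the condition which that sentence sets.

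**What to change.** - In the amended plan of Section 7.1.1, add baseline PACS as a continuous covariate in the primary ANCOVA. In each secondary ANCOVA, add the baseline value of the same measure where one was collected.
- Carry this into the PPCP versus PLES comparison in Section 7.1.2, stating that the covariate is the value from before randomisation.
- In the missing-data sentence, refer to the ANCOVA and its covariates in place of the linear mixed model.
- Do not offer the superseded mixed model, restricted to baseline and 16 weeks with a free arm effect at baseline, as an equivalent. Step 4 shows that it is not.
- Make sure the SAP says the same, and settle it before the 16-week outcomes are analysed.

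The cost is a few sentences and one degree of freedom per model. No new data are needed.
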